Perampanel Titration and Cognitive Effects

Protocol Version 1.8 – 02 May 2022

NCT0441797

PROTOCOL FOR CLINICAL RESEARCH TRIAL

Protocol Version 1.8 – 02 May 2022

TITLE: Effects of Titration Rate on Cognitive and Behavioral Side Effects of Perampanel

BRIEF DESCRIPTION OF STUDY

This is a randomized, double-blind, parallel group design across different titration rates of perampanel in healthy volunteers. The study consists of 8 visits, 4 of which will occur at the participant's home, over a 7-week period. One hundred and three (103) normal healthy subjects will be treated with perampanel (PER) at one of four different titration rates: (1) 2mg/day PER for one week followed by 4mg/day PER for five weeks, (2) 2mg/day PER for two weeks followed by 4mg/day PER for four weeks, (3) 4mg/day PER for six weeks, or (4) placebo (0mg/day PER) for six weeks. Cognitive and behavioral function testing along with safety testing will be conducted at screening, pretreatment baseline, the end of each week during the titration and maintenance period.

TIME PERIOD AND NUMBER OF SUBJECTS

A. Anticipated Number of Subjects: 103 (to obtain 76 evaluable subjects)
B. Anticipated Duration of Study: 1 Year

DESCRIPTION OF MEDICATIONS

Generic	Strength and Dosage Form	Therapeutic Classification
PER	2 mg/capsule	Anticonvulsant

Prepared by:

[name]
Professor, Department of Neurology & Neurological Sciences
Stanford Comprehensive Epilepsy Center
Stanford University School of Medicine
[name]
[name]
Tel: [name]
Fax: [name]
[contact]

TABLE OF CONTENTS

	Page
I. BACKGROUND AND RATIONALE	3
II. STUDY QUESTION	4
III. STUDY OBJECTIVE	4
IV. STUDY DESIGN	4
V. STUDY POPULATION	
A. Number and type of subjects	4
B. Inclusion Criteria	4
C. Exclusion Criteria	5
VI. STUDY PROCEDURES	
A. Overview: time and events	5
B. Blinding and controls	6
C. Dosage regimen	6
D. Enrollment goals	6
E. Visit-specific treatment and evaluation sequence	6
F. Subject Reimbursement Rates	8
VII. NEUROPSYCHOLOGICAL TESTS	
A. Outline	9
B. Description of Individual Tests	9
VIII. STUDY MEDICATION	
A. Description	15
B. Packaging and labeling	15
C. Shipment and storage	15
D. Maintenance of medication dispensing records	15
E. Return of unused medication	15
F. Concomitant medication and therapy	15
VIII. CLINICAL AND LABORATORY MEASUREMENTS	
A. Clinical efficacy measurements	16
B. Clinical safety measurements	16
C. Adverse event procedures	17

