Studies examining the cognitive effects of perampanel suggest that measures of cognition are minimally affected by perampanel at maintenance therapeutic doses. A retrospective comparison of the cognitive effects lacosamide and perampanel suggests that neither have negative effects on cognition (Meschede et al., 2018). However, this study was confounded by several factors, such as the use of perampanel and lacosamide as adjunctive treatments. A prospective, long-term study of the cognitive effects of perampanel in adolescents did not show an impact on a global measure of cognition, measured by a change from baseline assessments (Piña-Garza et al., 2018). Similar findings were shown in adolescents in another randomized, controlled trial in which a global cognitive measure after adjunctive treatment with perampanel was not different from placebo ([name] et al., 2016).

Cognitive side effects of drugs are affected by ASM dose and titration. However, the effects of titration and habituation on the cognitive and behavioral side effects of drugs are not well established for most ASMs, especially in regards to the timing of such effects, with the possible exception of topiramate. The present label representation of all drug-related treatment emergent adverse effects (TEAEs) across the titration and maintenance phases of clinical trials overexpresses the ultimate expected TEAEs once titration is completed and time for habituation has occurred. A more realistic and pragmatic view of TEAEs would be to denote TEAEs leading to ASM discontinuation and then separate TEAEs occurring during titration and the remaining TEAEs at maintenance once titration and time for habituation have occurred.

The present investigation is a post-marketing study in healthy volunteers designed to provide more safety information on effects of perampanel dose and titration on cognitive and other side effects, employing a randomized double-blind parallel group design at different

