Subjects who have active suicidal ideation (answering “Yes” to questions 4 and/or 5 on the C-SSRS) will be evaluated by the Investigator. If the Investigator determines that a subject is at risk of suicide or self-harm, appropriate measures to ensure the subject’s safety and obtain mental health evaluation must be implemented and the Investigator should evaluate if the patient should be discontinued from the study.

This is a safety measure and is not used in the primary analysis.

2g. Adverse Events Profile (AEP)

The AEP measures patients' perception of adverse effects of antiepileptic drugs (Baker et al, 1997; Perucca et al, 2012). It has 19 items assessing the frequency of the most common adverse effects of antiepileptic drugs during previous weeks, using a four-point Likert scale. Item ratings can be added to obtain a total score of 19–76, higher scores indicating a greater burden of adverse effects.

2h. QOLIE-89

The QOLIE-89 inventory was developed to assess perception of quality of life issues in patients with epilepsy (Devinsky et al., 1995). It has 89 questions covering 17 different scales: health perceptions, overall quality of life, physical function, role limitations-physical, role limitations-emotional, pain, work/driving/social function, energy/fatigue, emotional well-being, attention/concentration, health discouragement, seizure worry, memory, language, medication effects, social support, and social isolation. These scales also are aggregated into an overall score. In the present study, we will employ only questions related to the subject's perception of their attention/concentration, memory, and language (Perrine et al., 1995; Elixhauser et al., 1999). The purpose of these measures in the present study is to allow us to compare subjective perceptions of cognitive side effects to objective performances (Marino et al., 2009). Where appropriate, ratings will be made based on the previous week, rather than previous 4 weeks as originally written in the QOLIE-89.

VIII. STUDY MEDICATIONS

A. Description

PER 2mg, 4mg, and placebos will be provided by Eisai or their designee. All ASM doses and placebos will be overencapsulated in matched opaque capsules.

B. Packaging and Labeling

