ANY MEDICALLY SERIOUS ADVERSE EVENT REQUIRES IMMEDIATE NOTIFICATION OF THE FDA BY THE INVESTIGATOR.

Any serious adverse event that occurs up to two weeks following study participation must also be reported.

Serious adverse events must be reported to the lead site principal investigator, [name], within 24 hours of the site becoming award of the SAE.

Serious adverse events must be reported to sites' institutional review boards (IRB) according to their IRB's regulations.

Specific procedures for Double-Blind Studies

Site personnel not involved in direct care of study subjects will generate a randomization code. In an acute medical emergency, the randomization code may be broken if this is considered essential for subject management. For this purpose, the sealed randomization code will be provided to the investigator by the site pharmacy. If the code is broken, a record of the date, time and reason must be put into writing and sent to Eisai. This letter will become part of the permanent study record.

All adverse events should be recorded on the appropriate Case Report Forms (CRF's) including date of onset and cessation, intensity and relationship to study drug. The action taken and clinical outcome of the adverse event will also be recorded.

The investigator will report all serious AE's to the FDA and to Eisai without delay.

D. Medication Compliance Assessment

Compliance is to be judged by questioning the patient at the clinic visit and by the non-blinded observer's inspection of medication returned and recording missed doses on the appropriate CRF. Repeated noncompliance, or the missing of all scheduled doses of medication for three (3) consecutive days (72-hour period) would be cause for removing the subject from the study. Subjects should take all doses for 3 days before visits when cognitive function testing occurs.

E. Subject Discontinuation Criteria

1. Although they may withdraw without prejudice at any time, every effort should be made to have subjects complete the study within the bounds of safety and provisions of informed consent.
2. The investigator may discontinue the participation of any subject in this study if:
 - a. Any clinically significant adverse experiences are observed.
 - b. The subject is grossly noncompliant.
 - c. The subject's health would be jeopardized by continued participation.

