 - d. Consent is withdrawn. Subjects will be encouraged to complete the study, although they may withdraw at any time without prejudice.
4. Subject replacement.

Subjects who are dropped from the study prior to completion of all cognitive testing will not be replaced.

Subjects who are withdrawn prior to completion of at least one set of cognitive testing on treatment drug (i.e., prior to visit 5/study week 3) may be replaced.

5. Follow-up of discontinued patients

Subjects who receive study drug and are discontinued from the study will have all safety assessments completed, including a complete physical examination and laboratory evaluation including chemistry, hematology with differential, urinalysis and urine pregnancy test as required at study termination. This testing should be done as soon as possible. Medical follow-up of any severe adverse events or clinically significant abnormal laboratory values will continue until the abnormality resolves, and adequate medical explanation is apparent. Such data will be provided to Eisai.

X. STATISTICAL EVALUATION

A. Sample Size

We assume that the 4 groups (3 PER treatments and a placebo group) are equally spaced (in terms of z-score) at the time point of maximum drug effects (end week 1 for 4mg group and end week 3 for titration to 2mg x2wks then 4mg group), with a maximum difference of 0.24 (which is the difference between the placebo group and treatment at max effect). We then assume that over the 4 visits after max drug effect the z-scores get closer together until

they are equal at the treatment week 6th. The calculation indicates that at least 18 subjects are needed in each group to have 80% power. Since there are 4 groups, the total sample at least finishing assessment at end of week 6 (event 8) would be $19 \times 4 = 76$. Enrollment will include 20% (n=15) more to account for dropouts prior to assessment at end of visit 2 (baseline), and ~15% (n=12) more for dropouts before end of event 8 (treatment week 6). Thus, the total enrollment sample will be 103 subjects.

In summary, the 4 total groups (3 PER treatment, 1 placebo) would need at least 19 subjects per group (76 total), and total enrollment would be rounded to 105 to account for dropouts.

B. Methodology for statistical analysis

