This method with a similar overall score has been employed in prior investigations. This approach avoids potential Type I errors from multiple statistical comparisons and Type II errors resulting from reduced statistical sensitivity as a result of correcting for multiple comparisons. Analyses of individual components of the computer and neuropsychological assessment are secondary endpoints meant to evaluate sensitivity of the primary endpoint and examine the pattern of neuropsychological effects. All other endpoints are supportive and are safety assessments. Hence no adjustments for multiplicity are planned. P-values for these safety variables are not meant to show superiority and thus testing each of these variables at the $p=0.05$ level without multiplicity adjustment is a more conservative approach, which is appropriate for safety assessments and for secondary analyses of the pattern of impairments. The importance of the results should be evaluated in terms of actual differences and the risk/benefits offered by the drug to the patients.

The secondary outcome variables will be:

1. Compare titration rates for changes from Baseline (visit 2) to the end of titration (study week 3) and end of maintenance (study week 6) using Z-scores from full neuropsychological battery. The outcome variable for this analysis will be an overall neuropsychological composite Z-score, calculated by averaging individual z-scores of the selected performance measures from the computerized cognitive test battery (i.e., z-scores for the domain scores for executive function and processing speed), the average for individual Z-scores for AEP, POMS, QOLIE-cognitive questions (average of 3 scores), and the noncomputerized cognitive scores (i.e., average of z-scores for MCG immediate, MCG delayed, SDMT, Stroop-average score).
2. Compare titration rates for TEAEs and dropouts due to TEAEs across visits 3-8 (i.e., weeks 1-6).
3. Separate comparisons of titration rates for behavioral overall scores and cognitive overall scores.
4. Comparisons of titration rates and habituation over time for individual measures.

Summary statistics will be calculated by treatment for each evaluation of antiepileptic blood levels (ABLs). Additional analyses of data will be performed which take the ABLs into account. Linear correlations of plasma concentrations and the overall composite and individual score variables will be plotted with a fitted regression line superimposed for each condition.

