The incidences of all adverse events reported during the trial will be tabulated by treatment and study period. The other safety variables, which include changes in hematology, clinical chemistry, and urinalysis parameters, and vital signs will be analyzed descriptively. The actual measurement and its change from baseline will be presented by visit and period of collection. In addition, shift tables may be used to evaluate the number and percentage of subjects having a different post-baseline status when compared with their baseline status.

C. Interim Analysis

No interim analyses are planned.

D. Definition of Evaluable Subjects

Any subject who ingested one or more doses of blinded study medication and provided follow-up information will be evaluable for the analysis of the safety data. The primary analysis will include subjects who complete all visits or at least one set of cognitive/behavioral testing on treatment drug and who did not have any important deviations, which may have an impact on cognitive function. Subjects who prematurely discontinue the study will be evaluated based on the data collected at each visit attended. Any subject who is evaluable for the safety analysis who also has baseline and end of drug period cognitive/behavioral data available will be evaluable for the intent-to-treat analysis of the parameters of interest. Any subject evaluable for the intent-to-treat analysis will be evaluable for the per-protocol analysis of the parameters of interest provided that the subject was compliant with the protocol with regard to the study medication regimen, use of concomitant medications, sleep requirements prior to cognitive testing, alcohol consumption, caffeine consumption, and use of OTC medications prior to cognitive testing. All data will be used to their maximum possible extent, but without any imputations for missing data for any parameter.

XI. REFERENCES:

1. Background References.

French, J. A., Krauss, G. L., Steinhoff, B. J., Squillacote, D., Yang, H., Kumar, D., & Laurenza, A. Evaluation of adjunctive perampanel in patients with refractory partial-onset seizures: results of randomized global phase III study 305. *Epilepsia* 2013;54(1), 117-125.

Krauss, G. L., Bar, M., Biton, V., Klapper, J. A., Rektor, I., Vaiciene-Magistris, N., ... & Kumar, D. Tolerability and safety of perampanel: two randomized dose-escalation studies. *Acta Neurol Scand* 2012a;125(1):8-15.

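### The adverse event table counts incidences by study period with no rule for continuing events, so it may not show which side effects remain at maintenance, as the rationale asks

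*Combined protocol and SAP*

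**What the plan says.** Section I (Background and Rationale) criticises labels that merge side effects over titration and maintenance. It would report TEAEs that lead to discontinuation, and then "separate TEAEs occurring during titration and the remaining TEAEs at maintenance once titration and time for habituation have occurred".

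Section X.B (Methodology for statistical analysis) has two relevant statements. The safety paragraph says: "The incidences of all adverse events reported during the trial will be tabulated by treatment and study period". Secondary outcome 2 reads: "Compare titration rates for TEAEs and dropouts due to TEAEs across visits 3-8 (i.e., weeks 1-6". Neither says what a study period is for adverse events. Neither says whether an event that begins in one period and continues into the next is counted in the second.

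The only boundary between titration and maintenance is in secondary outcome 1 of X.B, which compares all titration rates at "the end of titration (study week 3) and end of maintenance (study week 6". It is stated for the composite z-score, not for adverse events.

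Section IX.C (Adverse Event Procedures) has adverse events recorded on the CRF "including date of onset and cessation, intensity and relationship to study drug". The tables in VI.C and Appendix A show TEAEs assessed at all eight events. No section plans an analysis of TEAE duration, resolution or persistence.

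**The concern.** What remains at maintenance is a question about persistence: of the subjects in an arm at a given week, how many still have the event? Incidence in its usual sense answers a different question, namely how many subjects had a new onset in the period. A subject whose dizziness began in week 1 and never stopped has no new onset in weeks 4-6.

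The plan's own expectations make this matter. Section X.A places the maximum drug effect at "end week 1 for 4mg group and end week 3 for titration to 2mg x2wks then 4mg group", that is, at or before the week-3 boundary. If onsets cluster there, new-onset counts will be low in weeks 4-6 both when subjects habituate and when they do not. The rationale expects fewer side effects after titration, and a count by onset could appear to confirm that without testing it. The TEAE comparison is a listed secondary outcome, and its reading would be affected.

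**Working it through.** The documents give no adverse event rates, so there is no planned figure to reproduce. The check is a counting exercise under stated assumptions.

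**Inputs**
- Boundary: end of week 3 for every arm (X.B, secondary outcome 1), borrowed from the composite outcome. Each arm then has 21 days before it and 21 days after it.
- Subjects per arm: 19 (X.A). This is the completer target and serves only as a round denominator. The safety set in X.D is anyone who took a dose and provided follow-up.
- Share with onset in weeks 1-3: *p*, assumed 0.2 to 0.6.
- Share of those still affected at week 6: *f*, assumed 0 to 1.

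**Single case.** Ten of 19 subjects have onset in week 1 and all are still affected at week 6.
- New onsets in weeks 4-6: 0/19 = 0%.
- Ongoing at week 6: 10/19 = 53%.

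**Range, with no new onsets after week 3.** New onsets in weeks 4-6 = 0. Ongoing at week 6 = 19 × *p* × *f*.

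| *p* | *f* = 0 | *f* = 0.25 | *f* = 0.5 | *f* = 1 |
|---|---|---|---|---|
| 0.2 | 0 (0%) | 1.0 (5%) | 1.9 (10%) | 3.8 (20%) |
| 0.4 | 0 (0%) | 1.9 (10%) | 3.8 (20%) | 7.6 (40%) |
| 0.6 | 0 (0%) | 2.9 (15%) | 5.7 (30%) | 11.4 (60%) |

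The onset count for maintenance is 0 in all twelve cells, while the share still affected runs from 0% to 60%.

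**With some late onsets.** Let *q* = 0.05 (assumed) be the new-onset rate in weeks 4-6 among subjects with no ongoing event, and let those new events still be present at week 6. Then new onsets = (1 − *pf*) × *q*, and ongoing = *pf* + new onsets. For *p* = 0.4:

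| *f* | New onsets, weeks 4-6 | Ongoing at week 6 |
|---|---|---|
| 0 (all resolve) | 1.00 × 0.05 = 5.0% | 0 + 5.0% = 5.0% |
| 0.5 | 0.80 × 0.05 = 4.0% | 20% + 4.0% = 24.0% |
| 1 (none resolve) | 0.60 × 0.05 = 3.0% | 40% + 3.0% = 43.0% |

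Here the onset count ranks the scenarios in the wrong order: full persistence looks slightly better than full resolution, because subjects who already have the event cannot start it again.

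**The case against.** The strongest reply is that habituation is not left to the adverse event table. Study question 2 concerns neuropsychological effects and is analysed with weekly objective and subjective z-scores. The AEP is collected in every treatment week and enters the subjective score; as section VII.B describes it, "It has 19 items assessing the frequency of the most common adverse effects of antiepileptic drugs during previous weeks". Secondary outcome 4 adds habituation over time for individual measures. This stands in part, and it confines the gap to TEAEs. It does not close the gap: the AEP is a self-rated frequency score over 19 fixed items, and it does not count subjects with an ongoing TEAE or account for those who left because of one.

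A second reply is that *incidences* is undefined. A table of subjects with an event reported in a period could include continuing events. This also stands. A reader might infer that the table is bound to show a decline, but the documents support only that it could, if events are counted by onset. The fault is a missing counting rule, not a stated exclusion.

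Two further inferences should be resisted. One is that time at risk per period differs by arm, because one arm takes "3) 4mg/day PER for six weeks" with no titration step while the others step up after one or two weeks. No arm-specific boundary appears in the documents, and the one boundary they give is common to all arms and leaves 21 days on each side. If arm-specific boundaries were used, a week-1 onset in the 4 mg arm would fall in maintenance, and the 0/19 illustration would not apply to that arm. The other is that secondary outcome 2 pools weeks 1-6; its wording fits a visit-by-visit comparison equally well.

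**Conclusion.** The point holds in limited form. The rationale asks for TEAEs that remain at maintenance, and the statistical section plans no summary that clearly delivers them. If incidence is counted by onset with a week-3 boundary, the table cannot separate habituation from persistence: under the assumed rates, the same zero is compatible with 0% to 60% of an arm still affected at week 6. These percentages rest on assumed onset and persistence rates, on extending the composite outcome's boundary to adverse events, and on the usual meaning of incidence.

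The primary analysis and the weekly z-score analyses are untouched. It would be wrong to infer that the trial cannot study persistence of side effects: onset and cessation dates are collected, so only the analysis rule is missing. This is a cheap improvement, not a threat to the trial's main result.

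**What to change.** Amend section X.B as follows.

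1. Define the adverse event periods as weeks 1-3 and weeks 4-6 for all four arms, placebo included, matching secondary outcome 1.
2. Keep the incidence table and label it as new onsets.
3. Add, by arm and week (visits 3-8), the number and percentage of subjects with each TEAE ongoing, over the number still under observation, from the CRF onset and cessation dates.
4. For every arm, report the percentage of subjects with a TEAE starting in weeks 1-3 in whom it is still ongoing at week 6.
5. List TEAE discontinuations separately with their recorded resolution status. They should be neither assumed unresolved nor allowed to drop silently out of the weekly counts.

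Item 4 conditions on having had an event after randomisation and will rest on few subjects, so it should be read descriptively. Item 3 is the better comparison between arms.

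The cost is one paragraph, one extra table and a little programming. No new data, visits or subjects are needed.

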Subjects will be instructed to limit alcohol consumption to no more than ½ ounce of absolute alcohol equivalents per day (approximately one 12 oz. beer, or 1 mixed drink) and no more than 3 ounces per week. Regular consumption of caffeine is allowed but will be limited to two cups on test days. Subjects will be instructed not to consume alcohol 12 hours prior to cognitive and behavioral testing, , or take any over-the-counter medications for at least 72 hours prior to cognitive and behavioral testing. All concomitant medications will be recorded on the case report forms. Any concomitant medications and other agents, which are known to affect perampanel or have significant effects on cognition may not be taken during this trial. A partial list of examples include: anticholinergics, anticoagulants, antidepressants, antiepileptics, antipsychotics, anxiolytics, central nervous system depressants, corticosteroids, doxycycline, erythromycin, H2 antagonists, lithium, methylphenidate, narcotics, quinidine, reserpine, theophylline, and centrally active antihistamines.

IX. CLINICAL AND LABORATORY MEASUREMENTS

A. Clinical Efficacy Measurements (Study weeks -1, 0, 1, 2, 3, 4, 5, & 6)

Neuropsychological testing will be completed at screening (visit 1; study week -1), baseline (visits 2; study week 0), and each week of the ASM treatment period (visits 3-8; study weeks 1-6). The neuropsychological test results from the first screening testing (i.e., visit 1 at -1 weeks) will not be included in the analyses. All subjects will have at least 7 hours of sleep on the evening before the day of cognitive testing. (Note. If the subject does not get the required hours of sleep or takes non-approved medication, caffeine, etc., cognitive and behavioral testing will be rescheduled).

For detailed information regarding all of the cognitive tests refer to Section VII.

B. Clinical Safety Measurements

1. Physical Examinations (Study weeks -1, 3, & 6)

A complete physical and neurological examination will be performed during pre-study screening (visit 1; study week -1) and at the completion of the study (visit 8; study week 6) or early study discontinuation. Brief physical and neurological examinations will be performed at visit 5 (study week 3).

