The parameters of interest are listed in Section VII. Descriptive statistics will be used to provide an overview of the primary, secondary, and other variable results. For categorical parameters, the number and percentage of subjects in each category will be presented. The denominator for percentages will be based on the number of subjects appropriate for the purpose of analysis. For continuous parameters, descriptive statistics will include number of subjects, mean, standard deviation (SD), median, minimum, and maximum. Unless otherwise specified, baseline neuropsychological data will be based on the Visit 2 assessments.

Study question 1: What are the behavioral, cognitive or other side effects of perampanel at different titration rates in healthy volunteers?

The primary outcome variable will be the overall neuropsychological composite z-scores for the objective and subjective measures combined.

Study question 2: What is the time course of habituation to objective vs. subjective neuropsychological (e.g., cognitive and behavioral) side effects of perampanel?

The primary outcome variable will be the neuropsychological composite z-scores for the objective and subjective measures, which will be analyzed separately.

The objective measure z-score will be calculated by averaging overall computerized and noncomputerized cognitive z scores, which are calculated by averaging individual z-scores of selected performance measures from the computerized cognitive test battery (i.e., average of z-scores for the domain scores for executive function and for processing speed) and from the noncomputerized cognitive test battery (i.e., average of individual z-scores for MCG immediate, MCG delayed, SDMT, and Stroop-average score). The subjective measure z-score will be calculated by averaging the individual z-scores for AEP, POMS, and QOLIE-cognitive questions (average of 3 scores from QOLIE). These z-scores will be assessed by a 4 (titration rate) \times 6 (time: weeks 1-6) ANCOVA controlling for scores at Baseline (visit 2) using an intent-to-treat analysis for those receiving neuropsychological testing at least at the end of week one. Imputations will be employed for dropout after week one.

We will control for differences across groups in age, gender, and personal/family history of psychiatric disorders.

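### Section X.D removes the whole subject for test-day lapses although the outcome is scored weekly: explicitly in the per-protocol set, and possibly in the primary set through an undefined term that conflicts with X.B

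*Combined protocol and SAP*

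**What the plan says.** Section X.D (Definition of Evaluable Subjects) defines two sets with a deviation rule.

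- **Primary analysis.** Subjects need all visits, or at least one set of on-treatment testing, and must be subjects "who did not have any important deviations, which may have an impact on cognitive function". X.D neither lists such deviations nor says what makes one important.
- **Per-protocol.** Subjects from X.D's intent-to-treat set qualify if they complied with the medication regimen, the concomitant-medication rules and "sleep requirements prior to cognitive testing, alcohol consumption, caffeine consumption, and use of OTC medications prior to cognitive testing". No tolerance is given, and nothing limits the consequence to the visit concerned.

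X.D then closes with "All data will be used to their maximum possible extent, but without any imputations for missing data for any parameter". Section X.B describes the primary 4 × 6 ANCOVA over weeks 1–6 as "using an intent-to-treat analysis for those receiving neuropsychological testing at least at the end of week one", with no exclusion for deviations.

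The rules themselves are in VIII.F and IX.A: at least 7 hours of sleep the night before, at most two cups of coffee or equivalent on test days, no alcohol for 12 hours and no OTC drugs for 72 hours before testing. VIII.F also sets daily and weekly alcohol limits. On lapses, IX.A says: "If the subject does not get the required hours of sleep or takes non-approved medication, caffeine, etc., cognitive and behavioral testing will be rescheduled".

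**The concern.** The unit of exclusion does not match the unit of measurement. A short night before the week-4 test makes that test doubtful. It says nothing about the other five weeks, yet a subject-level rule discards all six.

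Three things are at stake.

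- **Information.** Small session-level lapse rates accumulate over six sessions into much larger subject-level losses. The enrolment allowance in X.A covers dropout only.
- **The primary population is not fixed.** Because the term in X.D is undefined and X.B has no such exclusion, the primary set could be settled after the data are seen.
- **Relation to treatment.** IX.C lists headache, nausea, vomiting and abdominal pain among the known effects of the drug, and these can prompt OTC use. Exclusion could then depend on arm, in a study whose subject is side effects.

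**Working it through.** **1. The plan's own figures.** X.A states that "at least 18 subjects are needed in each group to have 80% power" and plans 19 × 4 = 76 finishing week 6. The enrolment sum reproduces: 20% of 76 = 15.2 (15) and 15% of 76 = 11.4 (12), so 76 + 15 + 12 = 103. Both additions are for dropout; none is for deviations. The 18 cannot be reproduced, because X.A gives no SD, within-subject correlation or primary alpha.

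**2. Starting numbers per arm.**
- 19: week-6 completers. This suits the per-protocol set, which is drawn from X.D's intent-to-treat subjects, who need end-of-period data.
- 22: (76 + 12)/4, those present after baseline. This is closer to the X.D primary set, which needs only one set of on-treatment testing. Treating all 22 as having six sessions slightly overstates their exposure to lapses.

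**3. Loss under whole-subject exclusion.** Let p be the chance that a session has a lapse that is not caught by rescheduling and is counted as an exclusion. The documents give no value; 1–5% is assumed, with independence over the six on-treatment sessions (weeks 1–6, IX.A).

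Share of subjects lost = 1 − (1 − p)^6. Share of sessions lost under a session-level rule = p.

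| p | Subjects lost | Left of 19 | Left of 22 | Usable at one week, session rule, of 19 |
|---|---|---|---|---|
| 1% | 5.9% | 17.9 | 20.7 | 18.8 |
| 2% | 11.4% | 16.8 | 19.5 | 18.6 |
| 3% | 16.7% | 15.8 | 18.3 | 18.4 |
| 5% | 26.5% | 14.0 | 16.2 | 18.1 |

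The expected arm falls below 18 when p exceeds 1 − (18/19)^(1/6) = 0.9% from 19, or 1 − (18/22)^(1/6) = 3.3% from 22.

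**4. Allowing for rescheduling.** If 80% of lapses are caught before the test, the effective rate is 0.2p and the loss is 1 − (1 − 0.2p)^6.
- Lapses at 2%: 1 − 0.996^6 = 2.4%, leaving 18.5 of 19 or 21.5 of 22.
- Lapses at 5%: 1 − 0.99^6 = 5.9%, leaving 17.9 of 19 or 20.7 of 22.

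**5. Rough effect on power.** Take X.A's 80% at 18 per group as given and assume a four-group F test at 0.05 with equally spaced means 0, 0.08, 0.16 and 0.24. The SD that returns 80% is then 0.223. This is a calibration and not the plan's own calculation. With it, whole-subject exclusion at p = 2% and 5% gives about 77% and 67% power from 19 per arm, or about 84% and 75% from 22. Session-level exclusion from 19 gives about 82% at p = 2% and 80% at p = 5%.

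**6. Which lapses escape rescheduling.** IX.A can act only on a lapse known before the test. Four of the six on-treatment tests are done at home. VI.E records the time of testing and the last two doses. VIII.F records concomitant medication. Appendix A requires a call for each home test to check adherence, but does not say that it precedes the test. Neither VI.E nor Appendix A lists a record of sleep, caffeine or alcohol at each session.

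**The case against.** The strongest reply is that the primary analysis may not be affected at all. Sleep, alcohol, caffeine and OTC use are named only in the per-protocol sentence. A reader might infer that X.D drops subjects from the primary analysis for one short night, but the documents do not say so: the primary sentence lists no items and requires the deviation to be important. On X.B's wording there is no deviation exclusion, and the primary loss is zero. This stands. What remains is that the term is open, that IX.A treats these same lapses as grounds for not testing, and that X.B and X.D cannot both define the primary set.

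Second, safeguards exist: rescheduling, a window of ±3 days, adherence calls for home tests and recording of concomitant medication. A lapse known beforehand is rescheduled, and one never recorded cannot exclude anyone. Only lapses discovered after the test count. This also stands, and it is why step 4 belongs beside step 3.

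Third, a per-protocol set defined by subject is a common supportive choice, and X.A's 18 is not stated as a requirement for that set. That is fair. But session-level handling of test-day lapses never keeps fewer data, and X.D itself asks for all data to be used as far as possible.

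Finally, setting a session to missing also conditions on something that happens after randomisation. That is correct, and it limits session-level exclusion to a supportive role.

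**Conclusion.** The point holds in limited form. X.D works at subject level with no visit-level rule. This is explicit for per-protocol and possible for the primary set, where the undefined term conflicts with X.B's intent-to-treat analysis and with X.D's closing sentence on using all data.

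The size depends on an uncaught lapse rate that the documents do not give. At an assumed 1–5%, 6–26% of subjects would be lost against 1–5% of sessions; with 80% of lapses caught at occurrence rates of 2–5%, the loss is 2.4–5.9%. All these figures assume independent lapses; lapses clustered in a few people would remove fewer subjects.

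Two stronger conclusions are not supported. A reader might infer that the arms will fall below the 18 used for power. From 19 completers that needs an uncaught rate above 0.9%, and from 22 above 3.3%; neither rate is known. A reader might also infer bias toward no difference. Drug-prompted OTC use makes treatment-related exclusion plausible, but nothing in the documents shows its direction or size.

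**What to change.** 1. In X.D, remove the deviation exclusion from the primary set, so that it matches X.B's intent-to-treat analysis.
2. For the per-protocol or a sensitivity analysis, set to missing only the session affected by a sleep, alcohol, caffeine or OTC lapse. Decide this blind to arm, and keep the subject's other weeks in a repeated-measures model that accepts missing weeks.
3. Exclude a whole subject from per-protocol only for non-compliance that spans sessions, such as with the medication regimen, and state the criterion beforehand.
4. Record four items at each session before testing: hours slept, caffeine that day, alcohol in the previous 12 hours and OTC drugs in the previous 72 hours. This also lets the existing rescheduling rule work for home tests.
5. Tabulate affected sessions by arm, so that any relation to treatment can be seen.

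The cost is a revision of X.D and four self-report items at sessions that already take place. The downsides are unbalanced weekly data and the remaining post-randomisation selection, so the session-level analysis should be labelled supportive. While X.D is open, its intent-to-treat definition (end-of-period data required) and its ban on imputation should also be reconciled with X.B, which asks only for week-one testing and plans imputation.
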